#### 14.3.9.1 Adverse events

AEs will be coded during the course of the trial according to Medical Dictionary for Regulatory Activities (MedDRA). AEs will be presented by preferred term and primary system organ class (SOC).

Treatment-emergent AEs will be summarised; however, all AEs recorded during the course of the trial will be included in subject data listings. The tabulations described in the following will only include the treatment-emergent AEs. In each of the tabulations, AEs are defined by MedDRA preferred terms within primary SOC.

AEs will be summarised in terms of the number of subjects with at least 1 event, the percentage of subjects with at least 1 event, the number of events, and the event rate per 100 patient years of observation time.

Related AEs are defined as AEs for which the investigator has not described the causal relationship to IMP as 'not related'.

An overall summary of the number of events and the number (percentage) of subjects with any treatment-emergent AEs, deaths, SAEs, permanent discontinuations from IMP, and/or withdrawals from the trial due to AEs, treatment-related AEs, mild and moderate AEs, and severe AEs will be presented.

Tabulations by SOC and preferred term will be presented for all AEs, SAEs, related AEs, and AEs leading to withdrawal from trial and/or permanent discontinuation of IMP. In addition, all AEs will be presented by severity and causal relationship to IMP, respectively.

The number of AEs and number of subjects with each type of AEs will be tabulated by treatment group from baseline to week 16, from baseline to week 32, and from week 17 to week 32.

AEs leading to withdrawal from trial and/or permanent discontinuation of IMP will be tabulated and listed. The detailed listing will provide an overview of the individual cases and include the age and sex of the subject, treatment received at the time of AE onset, the AE preferred and reported terms, causality and severity of the AE, the action taken with the IMP, AE outcome, start and stop date of AE, duration of AE, and number of days since first and last IMP administration. No narratives will be given.

SAEs will be evaluated separately, and a narrative will be given.

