#### 14.3.9.5 Anti-drug antibodies

For the exploratory endpoint

• Having a positive ADA response at weeks 0, 4, 8, 12, 16, 32, assessed separately.

the ADA status (positive vs. negative) including actual ADA titre at each assessment time point will be summarised. If considered relevant, descriptive statistics including number of subjects, mean, SD, median, and range of the actual ADA titres and visit will be provided. The ADA status across the trial for each subject (positive vs. negative) will also be classified and summarised.

The association of ADA status across the trial (positive vs. negative) with AEs/SAEs may be evaluated. In addition, the association of ADA titres (≥ median titre in positive subjects versus < median titre) with AEs/SAEs may be evaluated for ADA positive treated subjects only. The ADA positive subjects across the trial may also be divided into persistent positive versus transient positive. A subject will be considered as persistent positive if he/she has positive ADA for at least 2 consecutive visits with ADA assessment. Otherwise, the subject will be considered as transient ADA positive. The associations between ADA and AEs/SAEs may be summarised for both persistent positive subjects versus transient positives subjects.

For subjects who develop ADA, the change in EASI at end of treatment will be listed.

For ADA, all subjects with titre information will be listed. Graphical presentations may be performed.

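### The ADA section relates antibodies to EASI and adverse events without regard to order, and can list a week 16 EASI for a subject first positive at week 32

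*Combined protocol and SAP*

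**What the plan says.** ADA is an exploratory endpoint under the safety objective (Panel 3), defined in Section 14.3.9.5 as "Having a positive ADA response at weeks 0, 4, 8, 12, 16, 32, assessed separately". For each of those visits, "the ADA status (positive vs. negative) including actual ADA titre at each assessment time point will be summarised". Each subject also receives a single label: "The ADA status across the trial for each subject (positive vs. negative) will also be classified and summarised".

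That single label is what is set against safety: "The association of ADA status across the trial (positive vs. negative) with AEs/SAEs may be evaluated". The optional titre split and the persistent/transient split are also made per subject; for the latter, "A subject will be considered as persistent positive if he/she has positive ADA for at least 2 consecutive visits with ADA assessment". For efficacy the section specifies one output: "For subjects who develop ADA, the change in EASI at end of treatment will be listed". It adds "For ADA, all subjects with titre information will be listed".

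No sentence in the section requires an AE to start after the first positive sample. Developing ADA is not defined against the week 0 result, and the handling of a week 0 positive is not stated.

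Other sections bear on the point:
- Panel 2 schedules ADA at weeks 0, 4, 8, 12, 16 and 32. EASI is scheduled at screening and weeks 0, 1, 2, 4, 6, 8, 12 and 16, not at week 32.
- Section 9.2 places the last dose at week 14.
- Section 14.3.9.1 says of the AE tables: "The tabulations described in the following will only include the treatment-emergent AEs". Section 14.3.6 closes the treatment-emergent window 18 weeks after the last dose.
- Section 14.3.7 summarises EASI change at each visit and plots individual data.
- Section 14.3.4 rules out significance testing.

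**The concern.** Whether antibodies are followed by more adverse events or by loss of effect is a question of before versus after. A whole-trial label puts events from before and after seroconversion under one heading. A single end-of-treatment EASI change cannot show whether response fell after ADA appeared. Take a hypothetical subject at -90% at week 8, first positive at week 12 and at -75% at week 16: the listing shows only the last value, which reads as a good response. For a subject first positive at week 32, the listed EASI predates detection altogether.

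Section 5.5 discusses immunogenicity among the potential risks, and Section 12.2 gives its evaluation as the reason for collecting ADA. With about 8 LEO 138559 subjects and probably few positives, one subject whose sequence is misread could colour the whole description.

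**Working it through.** The plan states no figure on this point and has no power calculation, so there is nothing to reproduce. The check is one of timing.

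**1. Length of the AE window.** Last dose at week 14 (Section 9.2) plus 18 weeks (Section 14.3.6) = week 32. On schedule, the treatment-emergent window is weeks 0 to 32.

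**2. Where detection falls.** For a first positive at week w, the share of the window before detection is w/32. The EASI column compares w with week 16.

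| First positive (week) | Previous ADA sample (week) | Share of window before detection | First positive relative to the listed EASI |
|---|---|---|---|
| 4 | 0 | 4/32 = 12.5% | 12 weeks before |
| 8 | 4 | 8/32 = 25% | 8 weeks before |
| 12 | 8 | 12/32 = 37.5% | 4 weeks before |
| 16 | 12 | 16/32 = 50% | same visit |
| 32 | 16 | 32/32 = 100% | 16 weeks after |

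A subject first positive at week 32 also cannot be classed as persistent, because no scheduled ADA sample follows.

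**3. Dilution under the whole-trial label.** Assume a constant AE rate, full follow-up to week 32, and a rate multiplied by RR from ADA onset at week t. Relative to a subject without ADA, the whole-trial label shows

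ratio = (t + (32 - t) × RR) / 32.

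RR is not in the documents. The table uses assumed values of 3 and 2. Onset lies between the last negative sample and the first positive one, so both ends are shown.

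| First positive (week) | RR 3, onset at detection | RR 3, onset at previous sample | RR 2, onset at detection | RR 2, onset at previous sample |
|---|---|---|---|---|
| 4 | (4 + 28×3)/32 = 2.75 | 3.0 | (4 + 28×2)/32 = 1.875 | 2.0 |
| 8 | (8 + 24×3)/32 = 2.5 | 2.75 | (8 + 24×2)/32 = 1.75 | 1.875 |
| 12 | (12 + 20×3)/32 = 2.25 | 2.5 | (12 + 20×2)/32 = 1.625 | 1.75 |
| 16 | (16 + 16×3)/32 = 2.0 | 2.25 | (16 + 16×2)/32 = 1.5 | 1.625 |
| 32 | (32 + 0×3)/32 = 1.0 | 2.0 | (32 + 0×2)/32 = 1.0 | 1.5 |

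The onset-at-detection columns are therefore the lowest ratios the label would show, not point estimates.

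**4. No true effect.** With RR = 1 the formula gives (t + 32 - t)/32 = 1.0 for every t. Ignoring order does not by itself produce an association.

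**5. Would a single cut at the first positive sample be better?** Not reliably. For a first positive at week 32, all AEs from weeks 16 to 32 would be counted as before ADA, although antibodies could have been present for any part of those 16 weeks. For a first positive at week 16, the same holds for weeks 12 to 16, which include the week 14 dose. The interval between the last negative and first positive samples has to be kept apart.

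**The case against.** The best defence is that the time-resolved data are already planned. ADA status and titre are summarised at each visit, titres are listed by subject, AE start dates are recorded (Section 13.3), all AEs go into subject listings (Section 14.3.9.1), and individual EASI data are plotted (Section 14.3.7). With about 12 subjects the order can be worked out case by case. The AE association is optional, nothing is tested, and a statistical analysis plan still to be finalised before unblinding (Section 14.3.12) could add detail.

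Much of this stands, and it rules out several stronger readings that a reader might infer:
- *That the plan attributes earlier events or responses to ADA.* No sentence says so. The EASI output is a listing, and the AE association is something that may be done.
- *That AEs at any time are included.* The AE tables are restricted to treatment-emergent events, and Section 14.3.9.5 sets no window of its own.
- *That a loss of response is hidden.* It is absent from the ADA listing, but the individual EASI plots would show it.
- *That a false effect is created.* Step 4 shows otherwise. One could argue that stopping drug after an AE lowers drug levels and makes ADA easier to detect, but that depends on the assay's drug tolerance, which the documents do not give (Section 11.4.6 leaves method details to a bioanalytical report).

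The defence does not remove the core. No specified output puts the first-positive visit, AE onset and the EASI course side by side. The one mandatory ADA-EASI output is a single value, shows no ADA-negative subjects, and has no rule for a first positive at week 32.

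**Conclusion.** The point holds in a limited form. Section 14.3.9.5 relates ADA to outcomes without regard to order. The mandatory listing can pair a week 32 first positive with an EASI measured 16 weeks before detection, and the optional AE association uses a whole-trial label.

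The consequence for AEs is dilution of any real effect. Under an assumed threefold rate, the ratio shown ranges from 2.75 to 3.0 for a first positive at week 4, down to 1.0 to 2.0 for one at week 32, depending on when onset occurred. This rests on a constant AE rate and full follow-up as well as the assumed ratio. The week 32 mismatch with EASI needs no such assumptions; it follows from Panel 2.

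The impact is modest: ADA is exploratory, the analysis is descriptive, and about 8 subjects receive LEO 138559. The change is still worth making, because it uses data already collected and improves an output the plan commits to.

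**What to change.** Amend Section 14.3.9.5, or specify in the statistical analysis plan before unblinding:

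1. Replace the single-value EASI listing by a per-subject listing for all LEO 138559 subjects, with ADA-negative subjects as reference. Show ADA status and titre and EASI change at the shared visits (weeks 0, 4, 8, 12 and 16), the week 32 ADA result, the last-negative and first-positive visits, and AE onset dates.
2. Identify ADA development relative to the week 0 result, so that a subject already positive at baseline is distinguished from one who becomes positive later.
3. Mark a first positive at week 32 as *EASI effect not assessable*.
4. If the optional AE association is done, class AEs as before the last negative sample, between the last negative and first positive samples (order uncertain), or from the first positive sample. Do not use a single cut at detection.

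This needs no new samples or visits. The cost is wording, one reformatted listing and some programming. With few positives, the three AE classes will be sparse and should be read as case descriptions.

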#### 14.3.10 Pharmacokinetic analysis

The endpoint

• Serum concentration of LEO 138559 at weeks 0, 1, 4, 8, 12, 16, and 32, assessed separately.

will be evaluated based on the PK analysis set.

LEO 138559 serum concentrations will be listed and summarized by visit. The serum concentrations will be included in a cross-trial population PK analysis and reported separately.

## 14.3.11 Interim analysis

No interim analysis is planned.

## 14.3.12 General principles

All data will be analysed descriptively. No formal significance tests will be performed. Efficacy analyses will be based on the FAS, and safety analyses will be based on the safety analysis set. PK summary will be based on the PK analysis set.

If not mentioned otherwise, endpoints will be summarised descriptively at each visit by treatment. For endpoints evaluated over time, plots will be made to explore the trajectories with time.

An observed cases approach will be used for tabulations of data by visit (that is, involving only those subjects who attended each specific visit). The number of subjects for whom data was not collected at each specific visit will also be provided.

Categorical data will be summarised by treatment group, using the number and percentage of subjects in each category. Continuous data will be summarised using the mean, median, standard deviation (SD), 1st quartile, 3rd quartile, minimum, and maximum values. Additionally, geometric mean and coefficient of variation (CV) will be provided for the PK endpoint.

In general, for endpoints evaluated as change from baseline and/or where a baseline adjustment is applied, baseline is defined as assessments conducted at the randomisation visit (visit 3), if not otherwise stated. If the information is not available at the randomisation visit but at the (re)screening visit (visit 1) then this will be used instead.

All the analyses specified in the protocol will be reviewed in relation to the blinded data actually obtained, and the statistical analysis plan will be finalised before breaking the randomisation code.

Any changes from the statistical analyses planned in this clinical trial protocol will be described and justified in a protocol amendment, the statistical analysis plan, and/or in the CTR, dependent on the type of change.

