### 7.2 Number of subjects needed

This trial will be conducted at one site in Austria. Approximately 12 subjects will be randomised in a 2:1 ratio to LEO 138559 450 mg Q2W (8 subjects) and comparator 300 mg Q2W (4 subjects) to be able to achieve 12 subjects evaluable for the primary endpoint i.e., for whom a lesional biopsy is available at baseline and week 4.

Page 45 of 129

The statistical considerations for this sample size are described in Section 14.1.

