#### 9.5 Rescue treatment

In case subjects require additional treatment for atopic dermatitis during the treatment phase, as a first step, TCS / TCIs are recommended, and administration of study drug will be continued. Should other systemic AD therapy be required (e.g., cyclosporin A, oral JAK inhibitors, oral corticosteroids), the IMP administration should be stopped, and the subject will be withdrawn from the trial. Any use of AD therapy other than the trial treatment (see also section 9.7) needs to be documented in detail in the eCRF including use of emollients (see also section 9.4.)

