### 10.3 Early termination assessments

#### Permanent discontinuation of IMP

Subjects who permanently discontinue IMP for any reason will be asked to attend an early termination visit as soon as possible after last administration of IMP and return to the trial site for additional visits as indicated below:

- An early IMP termination visit as soon as possible after last dose of IMP (in case of early termination before week 4: a nominal week 4 visit)
- An end of trial visit (safety follow-up visit 16 weeks after last administration of IMP).

See the schedule of trial procedures (Section 4) for data to be collected at these visits. The subjects will be asked to complete the diary until end of trial visit. The investigator will review any AEs which will be followed up according to Section 13.7, if the subject agrees.

Details on data to be recorded in the eCRF for subjects who permanently discontinue IMP can be found in Section 11.8.

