## 14 Statistical methods

# 14.1 Sample size

The sample size of 12 subjects evaluable for the primary endpoint i.e., for whom a lesional biopsy is available at baseline and week 4 (8 receiving LEO 138559 and 4 receiving comparator) is based on the trial design for the exploratory comparison of the molecular signature changes of LEO 138559 and the comparator. The sample size is not based on power calculations.

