## 14.3.4 Testing strategy

No formal statistical significance tests will be carried out.

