## 14.3.7 Analysis of exploratory efficacy endpoints

## **Binary endpoints**

The endpoints

- Having a decrease in EASI of at least 50% (EASI 50) from baseline to week 1, 2, 4, 6, 8, 12, and 16, assessed separately.
- Having a decrease in EASI of at least 75% (EASI 75) from baseline to week 1, 2, 4, 6, 8, 12, and 16, assessed separately.
- Having a decrease in EASI of at least 90% (EASI 90) from baseline to week 1, 2, 4, 6, 8, 12, and 16, assessed separately.
- Having vIGA-AD score of 0 (clear) or 1 (almost clear) at week 1, 2, 4, 6, 8, 12, and 16, assessed separately.

will be analysed on the full analysis set by computing frequency tables for each time point by treatment group.

Proportions with respect to these endpoints will be plotted by treatment group.

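### As written, the observed-case rule takes subjects withdrawn for treatment failure out of the later EASI 50/75/90 and vIGA-AD 0/1 denominators, and no non-responder rule puts them back

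*Combined protocol and SAP*

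**What the plan says.** Section 14.3.7 covers four binary efficacy endpoints: EASI 50, EASI 75, EASI 90 and vIGA-AD 0/1, each at weeks 1, 2, 4, 6, 8, 12 and 16. They "will be analysed on the full analysis set by computing frequency tables for each time point by treatment group", and the proportions are plotted by arm. Section 14.3.12 sets the rule for by-visit tables: "An observed cases approach will be used for tabulations of data by visit (that is, involving only those subjects who attended each specific visit". It presents categorical data as counts and percentages, and it promises the number of subjects without data at each visit. Section 14.3.13 leaves missing values to the SAP. Its only rule of its own is the four-entry minimum for the weekly itch average.

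Section 9.5 states that if systemic AD therapy is needed, "the IMP administration should be stopped, and the subject will be withdrawn from the trial". Section 10.1 defines withdrawal as the end of IMP and of all further trial activities. For subjects who stop IMP without withdrawing, 10.3 provides "An early IMP termination visit as soon as possible after last dose of IMP" (a nominal week 4 visit if the stop is before week 4) and an end-of-trial visit. In Panel 2, EASI and vIGA-AD appear at the termination visit but not at the end-of-trial visit.

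**The concern.** These clauses together make some missing data depend on the outcome. A subject whose disease needs systemic therapy has failed on the allocated drug. The protocol ends that subject's visits, and the tables then count only attendees. The subject leaves the denominator at later visits without having been in the numerator there, so the percentage in that arm can only rise. The label in 14.3.7 is the full analysis set, but the percentage rests on those still attending.

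Section 12.1 makes Dupixent the reference for judging the efficacy of LEO 138559, and the reference arm is planned at 4 subjects. With no tests planned (14.3.4: "No formal statistical significance tests will be carried out"), the descriptive percentages and plots are the responder result. A difference between arms in efficacy-related withdrawal could therefore read as a difference in response.

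**Working it through.** **Inputs.** Section 7.2: "Approximately 12 subjects will be randomised in a 2:1 ratio to LEO 138559 450 mg Q2W (8 subjects", with 4 on comparator. At 2:1, 12 × 2/3 = 8 and 12 × 1/3 = 4, which agrees with the stated split. Section 14.1: "The sample size is not based on power calculations", so the plan offers no dropout or response rate to check against. The number of failures withdrawn, w, and the number of responders, r, are assumptions.

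**Formulas.** Let n be the arm size, r the responders at a later visit, and w the non-responders withdrawn before it.

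- Observed-case rate: r/(n − w)
- Rate with the failures kept as non-responders: r/n
- Difference: r·w / [n(n − w)]. It is never negative, and it is zero only if r = 0 or w = 0.

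**Results.**

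| Arm | r | w | Observed cases | Failures kept |
|---|---|---|---|---|
| n = 8 | 4 | 1 | 4/7 = 57.1% | 4/8 = 50.0% |
| n = 8 | 4 | 2 | 4/6 = 66.7% | 50.0% |
| n = 8 | 4 | 3 | 4/5 = 80.0% | 50.0% |
| n = 4 | 2 | 1 | 2/3 = 66.7% | 2/4 = 50.0% |
| n = 4 | 2 | 2 | 2/2 = 100% | 50.0% |

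**One withdrawal, any number of responders.** With w = 1 the difference is r/[n(n − 1)].

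- n = 8: from 1/56 = 1.8 points (r = 1) to 7/56 = 12.5 points (r = 7).
- n = 4: from 1/12 = 8.3 points (r = 1) to 3/12 = 25.0 points (r = 3).

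**Effect on the comparison.** Suppose half of each arm responds and one comparator failure is withdrawn. The table then shows 4/8 = 50.0% against 2/3 = 66.7%, a gap of 16.7 points with no difference in response.

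**How likely is at least one such withdrawal?** The documents give no rate. If each of 12 subjects independently had a chance q, the probability of at least one is 1 − (1 − q)^12: 46% for q = 5%, 72% for q = 10% and 93% for q = 20%. These values of q are assumptions.

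**Opposite case.** If the one subject lost from an arm of 8 with 4 responders were a responder who left for an unrelated reason, the observed-case rate would be 3/7 = 42.9% against 50.0%. The upward direction therefore belongs to the efficacy-failure route alone.

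**The case against.** The strongest reply is that the matter is open rather than settled. Section 14.3.13 sends missing values to the SAP, 14.3.12 lets the SAP be finalised up to unblinding, and the document reviewed contains no separate SAP text. This stands in part: a non-responder rule may yet be written. Until then, the observed-case rule is the one stated for these tables.

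A reader might infer more than the documents support, in four ways:

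- **That reported response rates will be inflated overall.** Sections 10.2.1, 11.4.4 and 11.4.5.2 also end treatment or participation for adverse events, ECG findings, pregnancy and symptomatic SARS-CoV-2 infection. Those exits can remove responders, so the net direction is not fixed. In addition, 9.5 puts topical therapy first with IMP continued, so withdrawal for systemic therapy is a second step. (Section 9.5 and the topical prohibition to week 16 in Panel 5 need to be reconciled; that is a separate matter.)
- **That termination-visit scores reach no by-visit table.** No clause says this. After a stop before week 4, 10.3 and Panel 2 note b provide a nominal week 4 visit whose scores can enter the week 4 table. For later stops the protocol is silent on visit mapping.
- **That these subjects cannot be identified without a new eCRF reason.** Section 9.5 requires other AD therapy to be documented in detail, and 9.7 requires prohibited treatments to be recorded. The forms in 10.2.1 and 11.8 already list lack of efficacy, and 10.2.1 also lists prohibited medication.
- **That the arms are fixed at 8 and 4.** Sections 7.2 and 14.1 aim for 12 subjects evaluable at week 4, so the full analysis set may be larger.

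Disclosure also softens the problem. Missing counts by visit, withdrawal reasons by last visit and arm (14.3.1), and individual EASI plots let a careful reader approximate r/n. They do not change the printed percentages or the plotted proportions. Finally, the endpoints are exploratory and untested, and observed-case description is a legitimate supportive display.

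**Conclusion.** The point holds, with limits. On the text, subjects withdrawn because they need systemic AD therapy leave the later responder denominators, as do subjects who stop IMP for lack of efficacy and have no further efficacy visits. For that route the bias in the arm's later responder percentage is upward whenever the arm has a responder. One such loss costs about 7 points with 4 responders of 8, and about 17 points with 2 of 4. These sizes rest on an assumed number of withdrawals, on planned arms of 8 and 4, and on counting the withdrawn subject as a non-responder afterwards. The conclusion also depends on the SAP adding no rule. It does not extend to the net effect of all dropout or to the week 4 biopsy endpoint.

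**What to change.** Make the change in 14.3.7 and 14.3.12, or in the SAP, before the randomisation code is broken:

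1. For the four binary endpoints, keep every subject who withdraws or stops IMP for lack of efficacy or for systemic AD therapy in the full analysis set denominator, as a non-responder at all later scheduled visits. Identify them from the concomitant-therapy records and discontinuation reasons already in the eCRF; no new pick-list entry is needed.
2. Report subjects missing for other reasons separately, by count and reason. Show an all-FAS denominator only as a sensitivity display, because it treats these subjects as non-responders too and understates response when their absence is unrelated to efficacy.
3. Keep the observed-case table as supportive.

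This changes how subjects are counted and leaves every treatment and withdrawal rule as it is. The cost is a short addition to the text, one extra table and slightly less favourable responder rates.
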